**Table 6. Evaluation of Confirmed BOR**

Case	Overall response first timepoint	Overall response subsequent timepoint	Confirmed response/BOR
1	CR	CR	CR (if assessments at least 28 days apart). (note: sequence of CR – NE – CR would be considered as confirmed CR)
2	CR	PR	SD, PD, or PR 
 
If CR truly met at first timepoint, any subsequent assessment of PR should make the disease PD at that point. That is, neither a PR nor SD may follow CR.
 
Therefore, SD, if CR assessment <math>\geq 6</math> weeks (42 days after date of first treatment), otherwise PD.
 
However, BOR may be PR if subsequent scans suggest small lesions were still present at first assessment (in which case first assessment of CR should be changed to PR)
 

3	CR	SD	SD or PD 
 
SD, if CR or SD assessment <math>\geq 6</math> weeks (42 days) after date of first treatment, otherwise PD
 

4	CR	PD	SD or PD 
 
SD, if CR assessment <math>\geq 6</math> weeks (42 days after date of first treatment), otherwise PD
 

5	CR	NE	SD or NE 
 
SD, if CR assessment <math>\geq 6</math> weeks (42 days after date of first treatment) otherwise NE
 

6	PR	CR	PR (if assessments at least 28 days apart).
7	PR	PR	PR (if assessments at least 28 days apart). (note: sequence of PR – NE – PR would be considered as confirmed PR) Where there are cases of more than one SD assessment between two PR assessments, then this should be discussed.
8	PR	SD	SD
9	PR	PD	SD or PD 
 
SD, if PR assessment <math>\geq 6</math> weeks (42 days after date of first treatment), otherwise PD
 

10	PR	NE	SD or NE 
 
SD, if PR assessment <math>\geq 6</math> weeks (42 days after date of first treatment), otherwise NE
 

11	SD	SD, PR, CR	SD
12	SD	PD	SD or PD 
 
SD, if SD assessment <math>\geq 6</math> weeks (42 days after date of first treatment), otherwise PD
 

Case	Overall response first timepoint	Overall response subsequent timepoint	Confirmed response/BOR
13	SD	NE	SD or NE • SD, if SD assessment $\geq$ 6 weeks (42 days after date of first treatment), otherwise NE
14	NE, -	SD	SD
15	CR, PR, SD	-	SD or NE • SD, if assessment $\geq$ 6 weeks (42 days after date of first treatment) and does not qualify for CR or PR, otherwise NE.
16	PD		PD. Ignore all assessments after initial overall response of PD.
17	NE	NE	NE Where all assessments are Not evaluable

For changes in target tumor size, spider and waterfall plots will be presented. For all response assessments, swimmer plots will be presented. Target and Non-Target Lesions response assessments and incidence of new lesions will be summarized by visit and listed. All response assessments will be listed.

#### 9.8.2 Duration of Response (DOR)

The duration of response (in months) is defined as the period from the date of initial confirmed PR or CR until the date of first radiographically documented progressive disease or death from any cause. Only patients with BOR of CR or PR (i.e. responders) will be included in the analysis of duration of response.

$$DOR = [(Date of first PD/death - Date of first recorded confirmed CR/PR) + 1] / 30.4375$$

Patients with no documented progression or death after CR or PR will be censored at the last available tumor assessment (last assessment that is CR, PR, or SD):

$$DOR = [(Date of last assessment - Date of first recorded CR/PR) + 1] / 30.4375$$

The analysis of DOR will be performed with a Kaplan-Meier method (product-limit estimates) and a summary of associated statistics will be presented including corresponding two-sided 95% CI. The CI for the median will be calculated according to Brookmeyer and Crowley and CI for the survival function estimates at Month 3, 6, 9, 12, and 18 will be derived using the log-log transformation (SAS PROC LIFETEST CONFTYPE=LOGLOG), only if there are sufficient data for responders. However, the final choice of timepoints may be updated dependent upon the data.

Part B, DOR will be compared between ulixertinib and physician's choice of treatment using a Log Rank test or other appropriate test if the proportional hazards assumption does not hold.

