Statistical analysis: The Full Analysis Set (FAS) will include all patients who received at least one dose of study medication. For Part B, analyses performed on the FAS will allocate patients' treatment group as randomized. The safety analysis set will include all patients who received at least one dose of study medication. For Part B, analyses performed on the safety population will allocate patients' treatment group as actually received. The per-protocol (PP) analysis set will include all patients of the FAS who completed the study without any major protocol deviations. All analyses will be performed separately for Part A and Part B, and by group/tumor histology. Efficacy analysis: The efficacy analysis will be performed on the FAS. ORR is defined as the percentage of patients achieving a BOR of confirmed complete response (CR) and/or partial response (PR) as assessed by the investigator for Part A, and both as assessed by the investigator and as adjudicated by the independent review committee for Part B. ORR will be calculated with the corresponding 95% confidence interval (CI). For Part B, ORR will be compared between ulixertinib and physician's choice of treatment using a Chi square test. DOR is defined as the time from first response to disease progression or death. PFS is defined as the time from first day of trial medication to disease progression or death. OS is defined as the time from first day of trial medication to death. Censoring rules will be applied as appropriate. DOR, PFS, and OS will be analyzed using Kaplan-Meier estimates and curves, median PFS and respective 95% CIs. For Part B, DOR, PFS, and OS will be compared between ulixertinib and physician's choice of treatment using a Log Rank test. These analyses will be performed based on investigator assessment for Part A, and both on adjudicated assessment by the independent review committee and on investigator assessment for Part B. Sensitivity analyses will be conducted. Safety analysis: The safety analysis will be performed on the safety analysis set. AEs, including treatment-emergent adverse event, AEs considered study drug-related, deaths, SAEs, and AEs resulting in study drug discontinuation, will be summarized (number and percentage of patients) by System Organ Class and Preferred Term. The parameters associated with the clinical laboratory tests (hematology, clinical chemistry, and urinalysis) will be summarized with descriptive statistics by visit and for the change from baseline to each planned post-baseline visit. Graded laboratory abnormalities will be defined using the grading scheme based on NCI CTCAE and summarized. Shift tables will also be produced.		

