11.5.5.2 Part B

The primary endpoint for Part B is the Progression-Free Survival over 18 months (PFS), defined as time from first day of trial medication to disease progression as adjudicated by the independent review committee or death. Patients with no event will be censored at the last available tumor assessment. PFS will be analyzed using Kaplan-Meier estimates and curves, median PFS and respective 95% CIs.

For each histology, PFS curves will be compared between ulixertinib and physician's choice of treatment using Log Rank Test. The hazard ratio including 95% CI will be calculated by Cox's Proportional Hazards model.

Sensitivity analyses of the primary analysis will include similar analyses based on investigator response assessment and using PP analysis set.

Analyses of secondary efficacy endpoints will include analyses similar to PFS analysis for:

- Overall survival over 18 months (OS): time from first day of trial medication to death. Patients with no event will be censored at the last date the patient is known to be alive.
- Duration of response (DoR): time from first response to disease progression or death. Patients with no event will be censored at the last available tumor assessment. This analysis will be based on assessment as adjudicated by the independent review committee and replicated on investigator assessment.
- Overall response rate (ORR), defined as the percentage of patients achieving a BOR of confirmed CR and/or PR, will be presented with its 95% CIs and compared between ulixertinib and physician's choice of treatment using a Chi-square test. This analysis will be based on assessment as adjudicated by the independent review committee and replicated on investigator assessment.

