#### *Part B*

Part B sample size estimation may be updated after Part A results are available.

Approximately 80-100 patients will be randomized, using a 2:1 ratio, for each histology group in Part B.

Using a 2-sided, log-rank test with a 5% alpha, and assuming a median PFS of 1.7 to 8.5 months (depending on histology) in the physician's choice arm and twice as long on the ulixertinib arm, approximately 80 to 100 patients will be required in each group to achieve 80% power to show a statistically significant difference between the arms. This also assumes that each group will take approximately 24 months to accrue, and the analysis is expected to be performed 18 months following the last patient accrued. The anticipated loss to follow-up is estimated to be 10%.

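### Part B compares duration of response between arms by log-rank test, and by implication a Cox hazard ratio, among responders only; this is not a randomised comparison and should be descriptive

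*SAP*

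**What the plan says.** SAP 9.8.2 defines the DOR population: "Only patients with BOR of CR or PR (i.e. responders) will be included in the analysis of duration of response". For Part B it then states that "DOR will be compared between ulixertinib and physician's choice of treatment using a Log Rank test", with the qualifier "or other appropriate test if the proportional hazards assumption does not hold".

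The protocol plans the same comparison. The synopsis (3.1) says: "For Part B, DOR, PFS, and OS will be compared between ulixertinib and physician's choice of treatment using a Log Rank test". Protocol 11.5.5.2 lists DOR as a secondary endpoint under the lead-in "Analyses of secondary efficacy endpoints will include analyses similar to PFS analysis for". In that section the PFS analysis is a Kaplan-Meier summary, a log-rank test and a Cox hazard ratio for each histology. DOR is defined there as "time from first response to disease progression or death". It is to be analysed on independent review and repeated on investigator assessment.

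On size, SAP 6.4 says: "Approximately 80-100 patients will be randomized, using a 2:1 ratio, for each histology group in Part B". The power statement that follows concerns PFS. Neither document gives a power, event count or sample size for DOR, labels the DOR comparison descriptive, adjusts for selection, or plans a counterpart that includes non-responders.

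**The concern.** Randomisation makes the arms comparable at baseline, not among patients selected by what happens afterwards. Response is an outcome that Part B itself compares between arms. If ulixertinib changes who responds, the two responder groups are different kinds of patient, and a difference in their DOR mixes the drug's effect with that selection.

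Suppose ulixertinib produces every response that control would produce, plus extra responses in tumours that are harder to hold. Its average DOR then falls because it has done more. Selection can also work the other way and flatter the drug. At stake is a p-value and hazard ratio, reported beside the PFS and OS results, that a reader could take for randomised evidence.

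**Working it through.** **1. The plan's own figure (PFS).** Inputs from SAP 6.4: two-sided 5%, 80% power, 2:1 allocation, median doubled (hazard ratio 0.5), control median 1.7 to 8.5 months, 24 months of accrual, 18 months of further follow-up.

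Events = (1.960 + 0.842)² / [(2/3)(1/3)(ln 2)²] = 7.849 / 0.1068 = 73.5, so 74.

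With exponential PFS and no loss, the event probability is 0.997 at median 1.7 and 0.762 at 8.5. So N = 74/0.997, rounded up to 75, and 74/0.762, rounded up to 98. Treating 10% loss over 42 months as a hazard gives 76 and 100. The stated 80 to 100 is reproduced for PFS.

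**2. How many patients the DOR test would compare.** The documents give no Part B response rates. I assume 40% on ulixertinib and 20% on control, which are the Part A alternative and null rates (SAP 6.4), and vary control from 10% to 30%.

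- N = 100: 66.7 × 0.40 = 26.7 versus 33.3 × 0.20 = 6.7 responders.
- N = 80: 53.3 × 0.40 = 21.3 versus 26.7 × 0.20 = 5.3 responders.

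**3. Power for a true doubling of DOR.** Treat every responder as having an event, which is the most favourable case. The responder split is 0.8 to 0.2, whose product is 0.16. Power = Φ(√(D × 0.16) × ln 2 − 1.96).

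- N = 100: D = 33.3, so Φ(1.601 − 1.96) = 0.36.
- N = 80: D = 26.7, so Φ(1.432 − 1.96) = 0.30.

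The same formula, with the product of the split recalculated, gives these values at other control rates. At 10% it is 22% (N = 100) or 19% (N = 80); at 30% it is 46% or 39%. With censoring and a control median DOR of 12 months, simulated power at 40% versus 20% is 13% to 14%. This step measures imprecision only.

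**4. Can the test point the wrong way?** Assumed strata: some patients respond on either arm (median DOR 12 months), and others respond only on ulixertinib. No patient does worse on ulixertinib. The log-rank test is applied to responders only, with 60 versus 30 patients and 6,000 simulated trials per row. Control response is 20% and ulixertinib 40% unless stated.

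| Scenario | Points against ulixertinib | Significant against | Significant for |
|---|---|---|---|
| Extra responders, median 3 months | 83% | 13.6% | 0.5% |
| Extra responders, median 6 months | 71% | 7.0% | 1.6% |
| Median 3 months; the others' DOR 25% longer on ulixertinib | 77% | 8.0% | 0.6% |
| Median 3 months; control response 10% | 86% | 17.2% | 1.4% |
| Median 3 months; control response 30% | 69% | 6.3% | 1.1% |
| Same 12-month median for all responders | 47% | 1.4% | 5.5% |

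The nominal rate in each direction is 2.5%. Over N = 80 to 100, wrong-direction significance in the first five scenarios runs from 5.5% to 19.6%. When all responders share one distribution it is 1.4% to 2.5%. A separate run of the 60 versus 30 case, with censoring spread uniformly from 16 to 40 months after response, gave 13.3% and 6.7% for the first two rows. With 6,000 versus 3,000 patients, all 50 simulated trials were significant in the wrong direction at both 3 and 6 months. Under these strata the effect is therefore bias, not chance.

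**5. The same effect in means.** Over a 16-month window, mean time in response for an exponential with median m is (m/ln 2)(1 − 2^(−16/m)). This is 10.44 months for m = 12 and 4.22 for m = 3.

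- All patients, non-responders counted as zero: 0.2 × 10.44 + 0.2 × 4.22 = 2.93 on ulixertinib, against 0.2 × 10.44 = 2.09 on control.
- Responders only: 2.93/0.4 = 7.33 on ulixertinib, against 10.44 on control.

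The ordering reverses. With m = 6 for the extra responders the figures are 3.55 against 2.09 for all patients, and 8.87 against 10.44 for responders.

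**The case against.** The strongest objection is that this test will not be run. SAP 7.2 records termination during Part A and an abbreviated, safety-focused report. The output list leaves every DOR table, figure and listing unmarked for the final analysis. SAP 4 and 7.2 also defer Part B detail to a later version. This stands, and it limits the point to the written plan and its reuse. It does not withdraw the text: SAP 2.0, revised for the termination, still states the comparison.

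Second, the bias rests on assumed strata. This stands too. A reader might infer that the test is bound to disfavour ulixertinib, or that low power itself shows bias. The documents support neither. They give no Part B response rates or DOR medians, the excess vanishes when responders share one distribution, and step 3 measures only imprecision.

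Third, DOR is secondary, no alpha control is claimed for it, and the table shell has no p-value row. That reduces the weight of the point. It does not settle intent, because the PFS and OS shells have no test row either.

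Two clauses in SAP 9.8.2 might seem to help. The fallback for non-proportional hazards changes the test but keeps the same selected patients. The condition on sufficient responder data sits with the Kaplan-Meier estimates, not with the between-arm test.

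**Conclusion.** The concern holds in a limited form. As written, Part B tests DOR between arms on a subset defined by a post-randomisation outcome, so the result would not be randomised evidence. The direction and size of any bias cannot be established from the documents. If the extra ulixertinib responders have median DOR of 3 to 6 months against 12, wrong-direction significance is about 5.5% to 19.6% instead of 2.5%; with one common distribution there is no excess. At the assumed 40% and 20% response rates the test is also weak, with power of at most about 36% at N = 100 and 30% at N = 80 for a doubled DOR. A reader might infer that this study's reported results are affected; they are not, because Part B is outside the final analysis. The plan should be corrected before any reuse. The PFS, OS and ORR comparisons are not restricted to responders and do not share this problem.

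**What to change.** Remove DOR from the log-rank sentence in protocol 3.1. In protocol 11.5.5.2, take it out of the list of endpoints analysed like PFS, which also removes the implied hazard ratio. Delete the between-arm sentence in SAP 9.8.2. In its place, report the Kaplan-Meier median DOR with 95% CI by arm among responders, labelled descriptive, with no p-value or hazard ratio. This is a wording change. It costs one secondary p-value, with its hazard ratio, per histology.

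An all-patient comparison of time in response, with non-responders counted as zero, is optional and is more than a wording change. It would first need four things stated:

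- the population, since the FAS contains treated patients only and the All Patients Set contains everyone who consented;
- a time horizon;
- a censoring rule;
- the handling of responses after crossover to ulixertinib.

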### 9.8.3 Progression-free Survival (PFS)

The PFS (in months) is defined as the time from the first ulixertinib dose until the first radiographically documented progression of disease or death from any cause, whichever occurs first.

$$PFS = [(Date of first PD/death - Date of first study treatment) + 1] / 30.4375$$

Patients with no documented progression or death will be censored at the last available tumor assessment (last assessment that is CR, PR or SD):

$$PFS = [(Date of last assessment where patient is PD free - Date of first study treatment) + 1] / 30.4375$$

For patients with no post baseline tumor assessment a censored PFS at day 1 will be considered.

$$PFS = (Date of first study treatment - Date of first study treatment) + 1$$

The analysis of PFS will be performed with a Kaplan-Meier method (product-limit estimates) and a summary of associated statistics will be presented including corresponding two-sided 95% CI. The CI for the median will be calculated according to Brookmeyer and Crowley and CI for the survival function estimates at Month 3, 6, 9, 12, and 18 will be derived using the log-log transformation (SAS PROC LIFETEST CONFTYPE=LOGLOG). However, the final choice of timepoints may be updated dependent upon the data.

For Part B, for each histology, PFS curves will be compared between ulixertinib and physician's choice of treatment using Log Rank Test or other appropriate test if the proportional hazards assumption does not hold.

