- ^a Patients will return to the clinic or will be contacted for a safety follow-up assessment 30 days \pm 3 days after the last dose of study drug was taken; or earlier if subsequent therapy for advanced malignancy is initiated prior to 30 days \pm 3 days.
- ^b Patients or their legally authorized representatives will be contacted every three months (\pm 7 days) until death, end of the study, or patient withdrawal of consent, whichever comes first. Survival and subsequent treatment status may be collected by public records, medical records, or by contacting the patient or their legally authorized representative by phone.
- ^c Full medical history at screening, only review/update of history at subsequent visits.
- ^d Oncologic history of the malignancy under study including prior regimens (duration of therapy, best response on therapy, date of discontinuation, and reason for discontinuation), surgery, and radiation therapy.
- ^e Physical examinations should be symptom driven after the Screening Visit.
- ^f Ophthalmological examinations will be performed by an ophthalmologist at screening, and whenever clinically indicated. In Part B, only patients in the ulixertinib arm need an ophthalmological exam. See section 10.1.5 for a full description of tests.
- ^g ONLY if the screening serum pregnancy test was performed more than 1 day previously.

- h After screening and baseline, if urine pregnancy test is positive, confirm with serum test.
- i Visit 2 clinical lab samples should be collected pre-dose if not done during Screening Visit within 72 hours of start of treatment.
- j Chemistry, hematology, and urinalysis. After Cycle 2, clinical labs to be performed prior to starting each new cycle or more frequently when clinically indicated at the investigator's discretion. See section 10.1.6 for a full description of test.
- k Patients with a normal ECG in Cycle 1 do not need to have repeat ECGs in subsequent cycles. Patients should be supine for 5 minutes prior to the ECG.
- l Tumor assessments will be made prior to dose initiation, at Visit 5, and then every 2 cycles. Patients who discontinue treatment for reasons other than progression will have assessments at the EOT visit (unless their previous assessment was performed within 28 days). The same imaging modality used for an individual patient (i.e. CT or MRI) at Screening should be maintained throughout the study.

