9.2 PATIENT DISCONTINUATION CRITERIA

Treatment is to be discontinued for any of the following reasons:

- Disease progression (at the discretion of the investigator). If brain or bone metastases develop while on study, patients may be permitted to continue on study, after discussion with the medical monitor, if the overall risk/benefit is still favorable.
- Unacceptable toxicity.
- Changes in the patient's condition which render the patient unacceptable for further treatment (at the discretion of the investigator).
- Investigator's judgement.

Patients who have been discontinued from treatment should still be followed for survival.

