10.1.9 Disease Status

The decision for body areas to be scanned will depend on the extent of disease. Disease assessments must include all known or suspected disease sites. Imaging will be performed on the abdomen, chest, pelvis, and the site of the primary tumor if elsewhere.

Tumor measurements based on physical examination will occur at baseline and on the first day of each treatment cycle. Tumor assessments will be made by CT/MRI/Physical Exam prior to dose initiation, at the 1st protocol-specified tumor measurement evaluation at the beginning of Cycle 2 and then every 2 cycles, and at End of Treatment. Patients that discontinue study treatment for any reason other than disease progression, must continue to have disease assessments every 8 weeks (\pm 7 days) until disease progression or the initiation of subsequent anticancer therapy. The schedule of tumor assessments should be fixed according to the calendar, starting with cycle one day one, regardless of treatment delays or interruptions due to toxicity. The same imaging technique used to characterize each identified and reported lesion at baseline will be employed in the following tumor assessments.

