11.5.5.1 Part A

The primary endpoint for Part A is the overall response rate (ORR) within a group. It will be defined as the percentage of patients achieving a BOR of confirmed CR and/or PR as assessed by the investigator. The ORR will be presented with its 95% confidence intervals (CIs).

All response assessments will be presented using swimmer plots and will be listed by patient.

Sensitivity analyses of the primary analysis will include similar analyses using PP analysis set.

Analyses of secondary efficacy endpoints will include Kaplan-Meier estimates and curves, median DoR and respective 95% CIs for analysis of:

- Duration of response (DoR): time from first response to disease progression or death. Patients with no event will be censored at the last available tumor assessment. This analysis will be based on investigator assessment.
- Progression-free survival over 18 months (PFS): time from first day of trial medication to disease progression or death. Patients with no event will be censored at the last available tumor assessment. This analysis will be based on investigator assessment.
- Overall survival over 18 months (OS): time from first day of trial medication to death. Patients with no event will be censored at the last date the patient is known to be alive.

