### 9.8.1 Overall Response Rate (ORR) / Best Overall Response (BOR)

Tumor response will be assessed by the Investigator using RECIST 1.1 criteria.

The decision for body areas to be scanned will depend on the extent of disease. Tumor assessments must include all known or suspected disease sites. Imaging will be performed on the abdomen, chest, pelvis, and the site of the primary tumor if elsewhere. Tumor measurements based on physical examination will occur at baseline and on the first day of each treatment cycle.

Tumor assessments will be made by CT/MRI/Physical Exam prior to dose initiation, at the 1st protocol-specified tumor measurement evaluation at the beginning of Cycle 2 and then every 2 cycles, and at End of Treatment. Patients that discontinue study treatment for any reason other than disease progression, must continue to have disease assessments every 8 weeks ( $\pm$  7 days) until disease progression or the initiation of subsequent anticancer therapy. The schedule of tumor assessments should be fixed according to the calendar, starting with cycle one day one, regardless of treatment delays or interruptions due to toxicity. The same imaging technique used to characterize each identified and reported lesion at baseline will be employed in the following tumor assessments.

Anatomical measurements (target lesions) will be documented during screening and each subsequent evaluation. Objective assessments will be performed during screening and before the first study drug dose of every other cycle, starting with cycle 2.

The table below provides a summary of the overall response status determination at each time point.

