**Table 5. Evaluation of Overall Response**

Target lesions	Non-target lesions	New lesions	Overall response
CR	CR (or no non-target lesions)	No	CR
No target lesion a	CR	No	CR
CR	NE b	No	PR
CR	Non-CR/non-PD	No	PR
PR	Non-PD and NE (or no non-target lesions) b	No	PR
SD	Non-PD and NE (or no non-target lesions) b	No	SD
Not all evaluated	Non-PD	No	NE
No target lesion a	Not all evaluated	No	NE
No target lesion a	Non-CR/non-PD	No	Non-CR/non-PD
PD	Any	Yes or No	PD
Any	PD	Yes or No	PD
Any	Any	Yes	PD
No target lesion a	Unequivocal PD	Yes or No	PD
No target lesion a	Any	Yes	PD

CR = complete response, PR = partial response, SD = stable disease, PD = progressive disease, and NE = not evaluable.

aDefined as no target lesion at baseline.

bNot evaluable is defined as when either no or only a subset of lesion measurements is made at an assessment.

The ORR is defined as the percentage of patients having a confirmed response of either CR or PR. ORR will be calculated with the 95% confidence intervals (CIs). The 95% CIs will be estimated using the Clopper-Pearson method.

For Part B, ORR will be compared between ulixertinib and physician's choice of treatment using a Chi square test or Fisher's exact test as applicable.

Complete and partial response must be confirmed by a repeat assessment performed at > or = 4 weeks after the criteria for response are first met. Date of confirmed CR/PR will be the date of the first CR/PR that qualifies for confirmation. Additionally, patients with no post-baseline efficacy measurement due to reasons accountable for disease progression, will be assessed as non-evaluable and will count in the denominator of the ORR.

BOR will be assessed based on the tumor response at different evaluation time points from baseline until the first documented disease progression for RECIST or the last response assessment if there is no document disease progression at the time of the analysis. The order used to determine BOR is CR>PR>SD>PD, ignoring visits with missing tumor assessments. For SD to qualify for BOR, the SD assessment should be at least 6 weeks after first ulixertinib dose. BOR

date in this case will be the date of the first SD/PR/CR documented after 6 weeks.

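### SAP 9.8.2 and 9.8.3 restrict the PFS and DOR event to radiographically documented progression, which is narrower than the protocol's RECIST 1.1 event, contradicts the SAP's own formula, and if followed literally biases the Part A PFS outputs upward

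*SAP*

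**What the plan says.** **Protocol.** Section 11.5.5.1 defines Part A PFS as "time from first day of trial medication to disease progression or death". Sections 5.1.2 and 10.2.1 make this RECIST 1.1 progression, assessed by the local investigator. No sentence requires the progression to be seen on imaging. Section 10.1.9 allows assessment by CT, MRI or physical exam and adds that "Tumor measurements based on physical examination will occur at baseline and on the first day of each treatment cycle".

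**SAP.** Section 9.8.1 repeats the permitted methods: "Tumor assessments will be made by CT/MRI/Physical Exam prior to dose initiation". The event definitions then narrow. PFS runs "until the first radiographically documented progression of disease or death from any cause, whichever occurs first" (9.8.3) and DOR runs "until the date of first radiographically documented progressive disease or death from any cause" (9.8.2). The notes to Tables 14.2-1.4.1 and 14.2-1.5.1 and to Listing 16.2.6-6 carry the same restriction.

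Elsewhere the SAP is not restricted. The PFS formula in 9.8.3 uses the date of first PD or death, and the censoring sentence speaks of documented progression. Table 5 assigns an overall response of PD whatever the assessment method. Best overall response (BOR) is collected "until the first documented disease progression for RECIST or the last response assessment".

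SAP section 11 declares an added analysis population and reduced demographic reporting. It does not mention a narrower event.

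**The concern.** Progression shown by examination is an outcome the plan provides for. A palpable or visible lesion can be measured by exam, and a new lesion is progression under Protocol 10.2.1. Such a patient has an overall response of PD and BOR assessment ends there. Under the literal PFS definition, however, nothing has happened on that date. Unless a later image documents progression, the patient is either censored at the last assessment that was CR, PR or SD, or counted as an event only at death.

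Both outcomes push the Kaplan-Meier curve up, and the censoring is informative because it is triggered by the progression itself. Part A PFS on the full analysis set is retained in the final analysis as Table 14.2-1.5.1, Figure 14.2-1.6.1 and Listing 16.2.6-6. Because the formula and the prose differ, two programmers could also derive different event dates from the same record.

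**Working it through.** **1. Which rule applies to exam-documented PD**

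| Place | Is RECIST PD shown only by exam an event? |
|---|---|
| Protocol 5.1.2, 10.2.1, 11.5.5.1 | Yes |
| SAP Table 5 and BOR rule (9.8.1) | Yes, it is PD and ends BOR |
| SAP 9.8.3 formula and censoring sentence | Yes, if PD means overall response PD |
| SAP 9.8.2 and 9.8.3 opening definitions | No |
| Listing 16.2.6-6 note | Both: it gives PD or death as the event, then repeats the radiographic definition |

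So SAP 9.8.3 disagrees with the protocol and with itself.

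**2. Would a later scan pick the patient up?** Protocol 9.4 keeps the 8-weekly assessments only for patients who stopped for a reason other than progression. For the End of Treatment (EOT) visit the documents disagree. Footnote l of the Schedule of Activities says "Patients who discontinue treatment for reasons other than progression will have assessments at the EOT visit", which leaves progressors out. Protocol 10.1.9, Protocol 10.3.5 and SAP 9.8.1 place a disease assessment at End of Treatment with no such limit. An EOT assessment may itself be done by physical exam. A later image is therefore possible but not assured.

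**3. Size.** No figure in the plan depends on this point, so there is none to reproduce. The documents do not give q, the share of progressions that meet RECIST 1.1 but are shown only by exam. I take 5% to 30% as an assumed range, with exponential PFS.

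*(a) All such patients censored at progression.* The event hazard falls to (1 − q) times its true value, so the apparent median is the true median divided by (1 − q):

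| q | Factor 1/(1 − q) | Apparent median if true median is 3.5 months |
|---|---|---|
| 5% | 1.05 | 3.7 |
| 10% | 1.11 | 3.9 |
| 20% | 1.25 | 4.4 |
| 30% | 1.43 | 5.0 |

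*(b) Later deaths counted, as the SAP requires.* This is a simulation with true median 3.5 months, 18 months of follow-up, and assumed median survival after progression of 2 to 8 months. At q = 10% the apparent median is 3.8 to 3.9 months. Late events at death make up 6.5% to 9.4% of all patients, and 0.7% to 3.6% are censored. Of those censored, about 10% × 0.5^(18/3.5) = 0.3% of all patients would have progressed only after month 18 and would be censored under either rule. At q = 20% the apparent median is 4.1 to 4.5 months.

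*(c) Month-6 PFS with the scan schedule* (day 29, then every 8 weeks), true median 3 months, q = 20%. With deaths counted and no EOT rescue, the estimate is 37.5% to 41.9%, against 32.5% when the exam PD counts on its date. If 80% of these patients had PD documented at EOT (also an assumption), it would be 34.4% against 32.4%.

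**The case against.** The strongest reply is that the operative rules in 9.8.3 already use unqualified PD. A programmer who follows the formula, the censoring sentence and the swimmer-plot note would count exam-documented PD, and the bias would never arise. That is a fair reading, but it rests on ignoring the definition that opens the section and is repeated in the output notes. It shows an inconsistency to resolve before PFS is reported.

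A reader might draw stronger conclusions that the documents do not support:

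- *That every patient stopped for progression without a scan is lost by this wording.* Protocol PFS is also tied to RECIST 1.1. Progression judged clinically, without RECIST PD, is not an event under the protocol either, and removing one word does not change that. Only exam-measured RECIST PD is affected.
- *That no assessment follows once treatment stops for progression.* Three places schedule one at End of Treatment; only footnote l excludes progressors.
- *That these patients are mostly censored as event-free.* Survival follow-up runs 18 months from the start of therapy (Protocol 9.4) and death is an event, so in the simulations more of them become late events at death than are censored.
- *That many would be censored at day 1.* The first tumor assessment is at the start of Cycle 2, and no scheduled exam-only visit comes before it.
- *That Part B primary PFS or the delivered DOR is affected.* Part B primary PFS uses independent imaging review (Protocol 11.5.5.2, 12.1.5.2), where a radiographic event fits. The DOR table, figure and listing are not marked for the final analysis.

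It is also unclear how often exam-only PD would be recorded. Protocol 10.1.9 schedules exam measurements every cycle, but Schedule of Activities footnote e makes examinations symptom-driven after screening, and Protocol 10.3.3 lists disease status every second cycle with no exam.

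**Conclusion.** The concern holds in a limited form. The SAP's stated PFS and DOR event is narrower than the protocol's Part A event, conflicts with the SAP's own formula and with the PD that ends BOR, and is not declared as a change. Followed literally, it makes exam-documented RECIST PD a non-event or a late event at death unless a later image documents progression, and both biases run upward.

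The reach is Part A PFS: a secondary, descriptive endpoint without a formal test, in an abbreviated report focused on safety after early termination. The size cannot be fixed from the documents. At an assumed share of 5% to 10% of progressions, a true median of 3.5 months would appear as roughly 3.6 to 3.9 months. Larger shares give proportionately more, and EOT documentation gives less. These figures rest on exponential PFS and on assumed values for the share, the true median and survival after progression.

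**What to change.** 1. In SAP 9.8.2 and 9.8.3, and in the notes to Tables 14.2-1.4.1 and 14.2-1.5.1 and Listing 16.2.6-6, define the Part A event as the first RECIST 1.1 overall response of PD by any protocol-permitted method, or death. State that this is the same PD that ends BOR.
2. Add a sensitivity analysis of Part A PFS that counts treatment discontinuation for Progressive Disease without documented RECIST PD as an event. The reason for discontinuation is already collected and is tabulated in Table 14.1-1.1. This also keeps clinical-only progression visibly separate from the primary definition.
3. Reconcile Schedule of Activities footnote l with Protocol 10.1.9, Protocol 10.3.5 and SAP 9.8.1 on who has the EOT disease assessment. The report should state which rule sites followed, because it determines how many progressions could have been imaged.
4. If the radiographic restriction is intended for Part A, list it in SAP section 11 with its reason and align the formula, the censoring sentence and the BOR rule with it.

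The cost is wording, a small programming change and one extra output. No new data are needed. PFS may become slightly less favourable.
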